3.2.2. Quality of simulations

Data collection for the EG and the CG spanned from student enrollment to the conclusion of the 5-week intervention period. For the EG, both pre-test and post-test assessments were conducted, while the CG underwent only post-test evaluation.

Following the individual and group debriefings, the *Educational Practices Questionnaire (student version)* (EPQ) was administered. This questionnaire comprises 16 items, each rated on two separate 5-point scales to assess both quality and importance. The Spanish version of the EPQ was validated with Cronbach's alpha coefficients of 0.86 and 0.91 for its respective scales (Román-Cereto et al., 2022).

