5.1. Primary outcomes

Univariate statistics will be performed for the learning and empathy outcomes. Continuous variables will be reported using summary measures (means or medians) and measures of dispersion (standard deviation or interquartile range). Categorical variables will be presented as frequencies and percentages.

For bivariate analyses, the chi-square test or Fisher's exact test will be employed for qualitative variables. The Shapiro-Wilk test will be used to assess the normality of quantitative variables. Intergroup analysis will then be conducted using Student's t-test for independent samples if distributions are normal, and the Mann-Whitney U-test for non-normal distributions. For intra-group analysis (pre-test vs. post-test), Student's t-test for paired samples will be applied for normal distributions, with the Wilcoxon signed-rank test used when this premise is not met. For relationships between quantitative variables, Pearson's correlation will be utilized for normal distributions, while Spearman's rank correlation will be used for non-normal distributions.

The level of significance or type I error to be used is 0.05. Likewise, the effect size will be determined in case of significant differences using Cohen's d, Rosenthal's r, Cramer's V, among others.

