5.2. Secondary outcomes

Self-confidence in learning, the quality of simulations, and satisfaction with simulations will be analyzed using the same statistical methods applied to the primary outcomes.

6. Missing data

No missing data occurred because outcome data were collected using online forms, where all items, except for two open-ended questions, were mandatory. Furthermore, the research team ensured that all participants submitted their responses on time throughout the study, thereby preventing attrition.

7. References

Alconero-Camarero, A. R., Cobo, C. M. S., González-Gómez, S., Ibáñez-Rementería, I., & Alvarez-García, M. P. (2019). Descriptive study of the satisfaction of nursing degree students in high-fidelity clinical simulation practices. *Enfermería Clínica*, 30(6), 404-410. <https://doi.org/10.1016/j.enfcl.2019.07.007>

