International Nursing Association for Clinical Simulation and Learning. (2021). Healthcare Simulation Standards of Best Practice. *Clinical Simulation in Nursing*, 58, 66. <https://doi.org/10.1016/j.ecns.2021.08.018>

Analytic Code

EFFECTIVENESS OF A MULTIMODAL INTERVENTION WITH SIMULATION FOR LEARNING HOME HEALTH NURSING CARE OF PATIENTS WITH MULTIMORBIDITY AND HEART FAILURE

Principal Investigator:

[name]

Principal Investigator

Assistant Professor

Faculty of Nursing. University of Cadiz
Algeciras, Spain

Protocol identification
number:

087_2024

ClinicalTrials.gov
identifier:

NCT06855719 (started: 2025-03-10)

Current state:

Statistical analysis completed and analysis code forwarded to Principal Investigator
(2025-06-30).

Statistical analysis software SPSS® v.24

Table of contents

1. Socio-demographic, academic, employment, family and care-related data.....	3
2. Learning.....	4
2.1. General data.....	4
2.2. Pre-post test.....	5
3. Empathy.....	6
3.1. General data.....	6
3.2. Pre-post test.....	6
4. Self-confidence in learning.....	7
4.1. General data.....	7
4.2. Pre-post test.....	8
5. Quality of simulations.....	9
5.1. General data.....	9
5.2. Pre-post test.....	10
6. Satisfaction on simulations.....	11
6.1. General data.....	11
6.2. Pre-post test.....	11
6.3. Final satisfaction.....	12

1. Socio-demographic, academic, employment, family and care-related data

* Encoding: UTF-8.

```
FREQUENCIES VARIABLES=Group
/ORDER=ANALYSIS.

FREQUENCIES VARIABLES=Age
/NTILES=4
/STATISTICS=STDDEV VARIANCE RANGE MINIMUM MAXIMUM SEMEAN MEAN MEDIAN MODE SUM SKEWNESS SESKEW
KURTOSIS SEKURT
/ORDER=ANALYSIS.

SORT CASES BY Group.

SPLIT FILE SEPARATE BY Group.

FREQUENCIES VARIABLES=Age
/NTILES=4
/STATISTICS=STDDEV VARIANCE RANGE MINIMUM MAXIMUM MEAN MEDIAN MODE SUM SKEWNESS SESKEW KURTOSIS
SEKURT
/HISTOGRAM NORMAL
/ORDER=ANALYSIS.

FREQUENCIES VARIABLES=Sex
/ORDER=ANALYSIS.

FREQUENCIES VARIABLES=Marital_status Household_members Usuar_residence Academic_level Occupation
/ORDER=ANALYSIS.

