5.2. Pre-post test

```
* Encoding: UTF-8.  
SPLIT FILE OFF.  
SORT CASES BY Group.  
SPLIT FILE SEPARATE BY Group.  
EXAMINE VARIABLES=PRE_Perception_D1 PRE_Importance_D2 POST_Perception_D1 POST_Importance_D2  
/PLOT NPLOT  
/STATISTICS NONE  
/CINTERVAL 95  
/MISSING LISTWISE  
/NOTOTAL.  
NPAR TESTS  
/WILCOXON=PRE_Perception_D1 PRE_Importance_D2 WITH POST_Perception_D1 POST_Importance_D2 (PAIRED)  
/MISSING ANALYSIS.  
SPLIT FILE OFF.  
NPAR TESTS  
/M-W= PRE_Perception_D1 PRE_Importance_D2 POST_Perception_D1 POST_Importance_D2 BY Group(1 2)  
/MISSING ANALYSIS.
```

6. Satisfaction on simulations

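### Effect sizes are tied to a significant p-value and no confidence interval for a between-group difference is planned, so a non-significant post-test comparison gets no planned estimate or precision

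*SAP*

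**What the plan says.** Section 5.1 sets the threshold: "The level of significance or type I error to be used is 0.05". It then states the effect-size rule: "the effect size will be determined in case of significant differences", and names Cohen's d, Rosenthal's r and Cramer's V as examples. For comparisons between groups it names only tests: Student's t or Mann-Whitney for quantitative variables, chi-square or Fisher for qualitative ones. Description is by "summary measures (means or medians) and measures of dispersion (standard deviation or interquartile range").

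Section 5.2 says that the three secondary outcomes "will be analyzed using the same statistical methods applied to the primary outcomes", so the rule reaches all five outcomes in section 3.

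The text plans no confidence interval for a between-group difference. In the Analytic Code the only between-group procedure is the Mann-Whitney test, for example "M-W= PRE_Perception_D1 PRE_Importance_D2 POST_Perception_D1 POST_Importance_D2 BY Group(1 2") in code section 5.2. The front matter of the code gives the status as "Statistical analysis completed and analysis code forwarded to Principal Investigator", dated 2025-06-30.

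**The concern.** The stated aim is to evaluate effectiveness. A p-value above 0.05 can mean that the groups hardly differ, or that the trial was too small to tell. An estimate with its interval separates the two, and the plan drops the estimate in exactly that case. The SAP gives no sample-size calculation (section 2.2) and calls the population relatively modest (section 4), so non-significant results have to be expected and will need interpreting.

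There is a second effect. If standardised effects are reported only for comparisons that crossed 0.05, the reported set is selected on size and overstates the effects on average.

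**Working it through.** The SAP states no sample size, target effect or SD, so it has no figure to reproduce. The check has five parts.

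**1. Is an interval planned anywhere?** The only interval keyword is `/CINTERVAL 95` in code sections 3.2, 4.2, 5.2, 6.2 and 6.3. Each time it is a setting of EXAMINE, run with the file split by group and with `/STATISTICS NONE`. It could at most concern the mean of one arm, and that output is suppressed. It gives no interval for a difference. The code requests no effect size at all. That silence is not used as evidence here; the finding rests on the text of sections 5.1 and 5.2.

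**2. How many comparisons?** Variables in the Mann-Whitney commands:

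| Code section | All | Post-test or final |
|---|---|---|
| 2.2 Learning | 8 | 4 |
| 3.2 Empathy | 2 | 1 |
| 4.2 Self-confidence (SCLS) | 6 | 3 |
| 5.2 Quality (EPQ) | 4 | 2 |
| 6.2 Satisfaction (ESSAF) | 2 | 1 |
| 6.3 Final satisfaction | 1 | 1 |
| Sum | 23 | 12 |

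The other 23 − 12 = 11 are pre-test contrasts and out of scope. Three of these (two EPQ, one ESSAF) have no planned control-group data: section 3.2.2 says "while the CG underwent only post-test evaluation", and section 3.2.3 says the same.

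**3. What does the rule withhold?** With n per arm and a two-sided 0.05 test (the SAP does not state sidedness), the cut-offs are r = 1.96/√(2n) and d = t(0.975; 2n − 2) × √(2/n). The values of n are assumed.

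| n per arm | r | d |
|---|---|---|
| 30 | 1.96/√60 = 0.253 | 2.002 × √(2/30) = 0.517 |
| 50 | 1.96/√100 = 0.196 | 1.984 × √(2/50) = 0.397 |
| 70 | 1.96/√140 = 0.166 | 1.977 × √(2/70) = 0.334 |

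Any observed effect below the cut-off gets no effect size. The cut-offs depend on n only, not on the true effect.

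**4. How strong is the selection?** In 40,000 simulated two-arm trials per setting (normal data, t-test, true d = 0.5), no effect size would be determined in 52% of trials at 30 per arm and in 23% at 60 per arm. Where one was determined, the mean |d| was 0.73 and 0.58. Over all trials it averaged 0.51 and 0.50.

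**5. What would a reader see?** Constructed example, 50 per arm, domain score 0–4 (assumed to be the sum of four yes/no items). Counts at scores 0/1/2/3/4:

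- A: 0/5/17/15/13 against 0/2/12/20/16. Means 2.72 and 3.00, SDs 0.97 and 0.86. The difference is 0.28 with SE 0.183, so the 95% interval is 0.28 ± 1.984 × 0.183 = −0.08 to 0.64. Mann-Whitney z = 1.47, p = 0.14, r = 1.47/√100 = 0.147.
- B: 0/4/14/19/13 against 0/4/13/19/14. Means 2.82 and 2.86, SDs 0.92 and 0.93. The difference is 0.04 with SE 0.185, so the 95% interval is −0.33 to 0.41. z = 0.24, p = 0.81, r = 0.024.

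All four arms have median 3 and quartiles 2 and 4 under the (n+1)p percentile rule. Reported as medians and quartiles, A and B look the same, and both would be non-significant with no effect size. In A the interval still allows a difference of 0.64 points on a 4-point range; in B it stops at 0.41. The Hodges-Lehmann shift is 0 in both, which matters for the fix.

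**The case against.** The strongest reply is that little is lost. The code requests means and SDs by arm for every one of the 12 comparisons, whatever the p-value. A reader given those could work out a difference and an approximate interval, and could tell A from B. That is correct, and it limits the finding to planned reporting. It does not remove it: section 5.1 allows a report of medians and interquartile range alone, and those do not permit the calculation.

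Other points stand in part:

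- The plan does not use the word only. Still, making effect size follow from a significant difference is naturally read as exclusive.
- Final satisfaction is not defined as an outcome in section 3. Without it the count is 11, not 12.
- The example is finely balanced. Under linear interpolation one arm of each pair has an upper quartile of 3.75. A and B still look identical to each other. The example shows that this can happen, not that it did.
- The analysis is complete, so an addendum cannot restore pre-specification. It can still remove the selection from the report, provided it is labelled honestly.
- The missing interval is an omission, whereas the conditional effect size is a stated rule. The rule carries the finding and the interval supports it.

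**Conclusion.** The concern holds. It should be corrected, but it does not threaten the validity of the tests: no p-value changes. Up to 12 post-test or final between-group comparisons fall under a rule that leaves them without a planned estimate or interval if they miss 0.05. At an assumed 30 to 70 per arm, that covers observed d up to about 0.52 to 0.33, or r up to about 0.25 to 0.17. These figures assume two-sided testing and equal arms, because the SAP states neither n nor sidedness. The conclusion rests on the text of sections 5.1 and 5.2 and on no sample-size figure.

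**What to change.** Issue a dated addendum that leaves the existing rule visible and adds:

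> For every post-test between-group comparison of a primary or secondary outcome, the effect estimate is reported regardless of the p-value, with a 95% confidence interval for the difference: mean difference (with Cohen's d) where the t-test is used; Hodges-Lehmann shift (with Rosenthal's r) where the Mann-Whitney test is used; difference in proportions (with Cramer's V) for dichotomous items. For the three learning domain scores the mean difference with its 95% confidence interval is also given, because ties can make the Hodges-Lehmann shift zero. Pre-test contrasts are excluded, including those on EPQ and ESSAF, for which the control group has no planned pre-test data.

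Give the mean difference also for the learning total and final satisfaction if these turn out to be scored in a few whole points. State whether final satisfaction counts as a secondary outcome. Label all these estimates as added after the analysis was completed on 2025-06-30. No interval is needed for d, r or V themselves.

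The cost is one paragraph and estimates for the 12 comparisons, plus the 14 yes/no learning items, for which the code now runs frequencies only. All come from existing data. The document does not show whether SPSS v.24 gives every interval directly, so this must be checked; each can be computed from the individual scores. The drawbacks are some extra output and the post hoc label.

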5.2. Secondary outcomes

Self-confidence in learning, the quality of simulations, and satisfaction with simulations will be analyzed using the same statistical methods applied to the primary outcomes.

6. Missing data

No missing data occurred because outcome data were collected using online forms, where all items, except for two open-ended questions, were mandatory. Furthermore, the research team ensured that all participants submitted their responses on time throughout the study, thereby preventing attrition.

7. References

Alconero-Camarero, A. R., Cobo, C. M. S., González-Gómez, S., Ibáñez-Rementería, I., & Alvarez-García, M. P. (2019). Descriptive study of the satisfaction of nursing degree students in high-fidelity clinical simulation practices. *Enfermería Clínica*, 30(6), 404-410. <https://doi.org/10.1016/j.enfcl.2019.07.007>

International Nursing Association for Clinical Simulation and Learning. (2021). Healthcare Simulation Standards of Best Practice. *Clinical Simulation in Nursing*, 58, 66. <https://doi.org/10.1016/j.ecns.2021.08.018>

Analytic Code

EFFECTIVENESS OF A MULTIMODAL INTERVENTION WITH SIMULATION FOR LEARNING HOME HEALTH NURSING CARE OF PATIENTS WITH MULTIMORBIDITY AND HEART FAILURE

Principal Investigator:

[name]

Principal Investigator

Assistant Professor

Faculty of Nursing. University of Cadiz
Algeciras, Spain

Protocol identification
number:

087_2024

ClinicalTrials.gov
identifier:

NCT06855719 (started: 2025-03-10)

Current state:

Statistical analysis completed and analysis code forwarded to Principal Investigator
(2025-06-30).

Statistical analysis software SPSS® v.24

Table of contents

1. Socio-demographic, academic, employment, family and care-related data.....	3
2. Learning.....	4
2.1. General data.....	4
2.2. Pre-post test.....	5
3. Empathy.....	6
3.1. General data.....	6
3.2. Pre-post test.....	6
4. Self-confidence in learning.....	7
4.1. General data.....	7
4.2. Pre-post test.....	8
5. Quality of simulations.....	9
5.1. General data.....	9
5.2. Pre-post test.....	10
6. Satisfaction on simulations.....	11
6.1. General data.....	11
6.2. Pre-post test.....	11
6.3. Final satisfaction.....	12

1. Socio-demographic, academic, employment, family and care-related data

* Encoding: UTF-8.

```
FREQUENCIES VARIABLES=Group
/ORDER=ANALYSIS.

FREQUENCIES VARIABLES=Age
/NTILES=4
/STATISTICS=STDDEV VARIANCE RANGE MINIMUM MAXIMUM SEMEAN MEAN MEDIAN MODE SUM SKEWNESS SESKEW
KURTOSIS SEKURT
/ORDER=ANALYSIS.

SORT CASES BY Group.

SPLIT FILE SEPARATE BY Group.

FREQUENCIES VARIABLES=Age
/NTILES=4
/STATISTICS=STDDEV VARIANCE RANGE MINIMUM MAXIMUM MEAN MEDIAN MODE SUM SKEWNESS SESKEW KURTOSIS
SEKURT
/HISTOGRAM NORMAL
/ORDER=ANALYSIS.

FREQUENCIES VARIABLES=Sex
/ORDER=ANALYSIS.

FREQUENCIES VARIABLES=Marital_status Household_members Usuar_residence Academic_level Occupation
/ORDER=ANALYSIS.

FREQUENCIES VARIABLES=Previous_Home_Health_Nursing Personal_Experience_Caring Caregiver_Exp
Simulation_Exp
/ORDER=ANALYSIS.
```

2. Learning

2.1. General data

```
* Encoding: UTF-8.  
SORT CASES BY Group Phase.  
SPLIT FILE SEPARATE BY Group Phase.  
FREQUENCIES VARIABLES=AO1 AO2 AO3 AO4 NI1 NI2 NI3 NI4 NI5 TC1 TC2 TC3 TC4 TC5  
/ORDER=ANALYSIS.  
FREQUENCIES VARIABLES=Total  
/NTILES=4  
/STATISTICS=STDDEV VARIANCE RANGE MINIMUM MAXIMUM MEAN MEDIAN MODE SUM SKEWNESS SESKEW KURTOSIS  
SEKURT  
/ORDER=ANALYSIS.
```

2.2. Pre-post test

* Encoding: UTF-8.

SORT CASES BY Group.

SPLIT FILE SEPARATE BY Group.

FREQUENCIES VARIABLES=PRE_AO PRE_NI PRE_TC PRE_Total POST_AO POST_NI POST_TC POST_Total

/NTILES=4

/STATISTICS=STDDEV VARIANCE RANGE MINIMUM MAXIMUM MEAN MEDIAN MODE SUM SKEWNESS SESKEW KURTOSIS

SEKURT

/ORDER=ANALYSIS.

FREQUENCIES VARIABLES=PRE_AO PRE_NI PRE_TC PRE_Total POST_AO POST_NI POST_TC POST_Total

/NTILES=4

/STATISTICS=STDDEV VARIANCE RANGE MINIMUM MAXIMUM MEAN MEDIAN MODE SUM SKEWNESS SESKEW KURTOSIS

SEKURT

/ORDER=ANALYSIS.

NPAR TESTS

/WILCOXON=PRE_AO PRE_NI PRE_TC PRE_Total WITH POST_AO POST_NI POST_TC POST_Total (PAIRED)

/MISSING ANALYSIS.

SPLIT FILE OFF.

NPAR TESTS

/M-W= PRE_AO PRE_NI PRE_TC PRE_Total POST_AO POST_NI POST_TC POST_Total BY Group(1 2)

/MISSING ANALYSIS.

3. Empathy

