3.1. Primary outcomes

3.1.1. Learning

Data collection for both the EG and the CG spanned from enrollment to the end of the 4-week intervention period, encompassing both pretest and post-test assessments.

Learning will be assessed through nursing students' performance during the simulations. Two independent observers, experienced in simulation-based teaching, evaluated each simulation (pretest and post-test) using a validated checklist specific to each scenario. The checklist measures the following aspects: (1) assessment of patients and home environment observation (4 items), (2) nursing intervention (5 items), and (3) transferable skills related to greeting, farewell, and communication (5 items). Each item is scored dichotomously (Yes/No), and a final overall evaluation (0-10 points) is provided. The inter-observer agreement will be determined by Cohen's kappa.

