3.2. Pre-post test

```
* Encoding: UTF-8.  
SORT CASES BY Group.  
SPLIT FILE SEPARATE BY Group.  
EXAMINE VARIABLES=Pretest Posttest  
/PLOT NPLOT  
/STATISTICS NONE  
/CINTERVAL 95  
/MISSING LISTWISE  
/NOTOTAL.  
NPAR TESTS  
/WILCOXON=Pretest WITH Posttest (PAIRED)  
/MISSING ANALYSIS.  
SPLIT FILE OFF.  
NPAR TESTS  
/M-W= Pretest Posttest BY Group(1 2)  
/MISSING ANALYSIS.
```

4. Self-confidence in learning

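### Section 5.1 lets a Shapiro-Wilk result choose the test, but the code for the primary learning outcome documents no normality check before its rank tests

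*SAP*

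**What the plan says.** SAP section 5.1 sets a sequence for both primary outcomes, learning and empathy. First, "The Shapiro-Wilk test will be used to assess the normality of quantitative variables". The result then decides the between-group test: "Intergroup analysis will then be conducted using Student's t-test for independent samples if distributions are normal, and the Mann-Whitney U-test for non-normal distributions". The within-group comparison follows the same logic: "Student's t-test for paired samples will be applied for normal distributions, with the Wilcoxon signed-rank test used when this premise is not met". On alpha, "The level of significance or type I error to be used is 0.05". Effect size is to be computed only after a significant result, with several measures offered and none fixed.

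Section 3.1.1 defines learning by a checklist of 4, 5 and 5 items: "Each item is scored dichotomously (Yes/No), and a final overall evaluation (0-10 points) is provided".

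The Analytic Code for learning (section 2.2, Pre-post test) issues one FREQUENCIES command twice on the pre and post scores. It then runs "WILCOXON=PRE_AO PRE_NI PRE_TC PRE_Total WITH POST_AO POST_NI POST_TC POST_Total (PAIRED" within groups and "M-W= PRE_AO PRE_NI PRE_TC PRE_Total POST_AO POST_NI POST_TC POST_Total BY Group(1 2" between groups. Empathy, the other primary outcome, has "EXAMINE VARIABLES=Pretest Posttest" with /PLOT NPLOT before its rank tests (Analytic Code, section 3.2).

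**The concern.** A rule that picks the test from the data can be audited only if the result that did the picking is on record. For learning it is not. FREQUENCIES with the listed statistics gives skewness and kurtosis, not Shapiro-Wilk, and the descriptive code in section 2.1 has no normality check either. A reader cannot tell whether the written rule was applied and led to rank tests, or whether rank tests were used without it.

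Two p-values and two effect measures, one pair from a t-test and one from a rank test, could then each be presented as the planned result for a primary outcome. Choosing the test from the data it is applied to is also avoidable, because a fixed analysis can be named in advance whatever the distribution.

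**Working it through.** **Text against code.** Commands in the Analytic Code, by outcome:

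| Outcome (code section) | EXAMINE /PLOT NPLOT | Tests that follow |
|---|---|---|
| Learning (2.2) | absent; duplicated FREQUENCIES in its place | Wilcoxon, Mann-Whitney |
| Empathy (3.2) | present | Wilcoxon, Mann-Whitney |
| Self-confidence (4.2) | present | Wilcoxon, Mann-Whitney |
| Quality of simulations (5.2) | present | Wilcoxon, Mann-Whitney |
| Satisfaction (6.2) | present | Mann-Whitney |
| Final satisfaction (6.3) | present | Mann-Whitney |

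Learning is the only outcome without the check. No t-test command appears in the listing, and the document gives no normality result for learning and no reason for the difference.

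**Could the missing check have changed the test?** The SAP gives no sample size, power figure or score distribution, so there is no stated figure to reproduce and the inputs below are assumptions.

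- Students per arm: n = 20, 30, 40 or 60.
- Mean item success: p = 0.5, 0.7 or 0.85.
- Scores: beta-binomial with intra-student correlation r = 0.1, so the beta parameters are a = p(1-r)/r = 9p and b = (1-p)(1-r)/r = 9(1-p). For p = 0.7, a = 6.3 and b = 2.7.
- Scales: 4 items, 5 items, and a total on 0-10 or 0-14. Both totals are tried because the code does not say how Total is formed.
- 2,000 runs per setting, both arms from the same distribution, Shapiro-Wilk at 0.05 in each arm.

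Percentage of runs in which both arms pass, which sends the written rule to the t-test:

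| Scale | p | n=20 | n=30 | n=40 | n=60 |
|---|---|---|---|---|---|
| 4 items | 0.5 | 15.3 | 0 | 0 | 0 |
| 4 items | 0.7 | 0 | 0 | 0 | 0 |
| 4 items | 0.85 | 0 | 0 | 0 | 0 |
| 5 items | 0.5 | 35.4 | 8.6 | 0 | 0 |
| 5 items | 0.7 | 2.5 | 0 | 0 | 0 |
| 5 items | 0.85 | 0 | 0 | 0 | 0 |
| Total 0-10 | 0.5 | 78.4 | 68.0 | 59.2 | 29.8 |
| Total 0-10 | 0.7 | 47.8 | 22.1 | 5.4 | 0 |
| Total 0-10 | 0.85 | 0.4 | 0 | 0 | 0 |
| Total 0-14 | 0.5 | 86.9 | 82.4 | 75.8 | 62.6 |
| Total 0-14 | 0.7 | 62.2 | 44.1 | 25.2 | 4.4 |
| Total 0-14 | 0.85 | 2.8 | 0 | 0 | 0 |

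At 40 or more per arm, the check would have sent the three subscales to rank tests. For the total score the answer depends on N and on how close scores lie to the ceiling, and the document gives neither.

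**Would a different test change the conclusion?** In simulations of a 0-10 score with 20-60 per arm and a real difference, the t-test and Mann-Whitney fell on opposite sides of 0.05 in roughly 3-8% of trials. At 40 per arm with no true difference, type I error stayed at 0.04-0.06.

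**The case against.** The strongest reply is that Wilcoxon and Mann-Whitney are what section 5.1 prescribes for non-normal scores. The code is labelled as that of a completed analysis, so it may simply show the branch taken. That stands in part. A reader might infer that text and code prescribe different primary analyses. The document shows only that the text is conditional and the learning code is not; the tests differ only if the learning scores would have passed Shapiro-Wilk, which is not reported.

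A reader might also infer that no normality check was run. The listing cannot prove that, because it is not a full log. It has no Cohen's kappa, chi-square or Fisher test, correlation or effect size, all of which the text plans, and no syntax that creates the pre and post variables. A repeated FREQUENCIES block where EXAMINE would stand looks like a copying slip. The supportable statement is that the check is not documented.

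A third tempting reading is that the rule has no answer when one arm looks normal and the other does not. The wording is loose, but the plural in the between-group sentence and the fallback in the within-group sentence are most naturally read as requiring normality throughout, with a rank test otherwise. Simulated disagreement between arms on a 0-10 score ran from 0% to about 60% depending on assumptions, so no single figure should be quoted for it.

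Finally, the gap concerns learning only. The empathy code contains the normality step.

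These replies do not supply the missing evidence. If the check was run and lost in copying, the document still needs the correction.

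**Conclusion.** The concern holds in this limited form: for one of two primary outcomes, the document does not support the choice of test that its own rule requires. Whether the test would have been different is unknown. On the assumed score model, the question is live mainly for the learning total and closed for the subscales at about 40 or more per arm.

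The statistical cost is modest. A reader might infer inflated type I error, but the simulations do not show it. The remaining cost is an unsupported primary test, an effect measure left open, and a small chance of opposite conclusions from the two candidate tests. All the percentages rest on assumed N, item success and intra-student correlation. The comparison of text with code rests on none of these.

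**What to change.** 1. Remove the normality gate from section 5.1. Name one between-arm analysis and one effect measure with 95% CI for learning, and the same for empathy, to be used whatever the distribution. The preferred choice is the post-test score adjusted for the pretest score in a linear model with robust standard errors, with Mann-Whitney as a sensitivity analysis. The pretest is already collected in both arms for both outcomes.
2. Replace the duplicated FREQUENCIES block in the learning code with the command for that analysis, and align the empathy code.
3. Section 5.2 borrows the methods of 5.1, so state there what carries over. Quality and satisfaction have no control-group pretest, so pretest adjustment cannot carry over to them.
4. The analysis is already complete, so issue this as a dated correction, label the adjusted model post hoc, and report the rank tests already run beside it.

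The minimum repair is to add EXAMINE /PLOT NPLOT for the learning scores and report its result with the test that it selects under the existing rule.

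The cost is some SAP wording, a few lines of SPSS and one re-run on existing data. No new data are needed. The price of the fuller repair is that the adjusted model cannot be presented as pre-specified.
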